### 9.3. Populations for Analyses

The following populations are defined:

Population	Description
Full Analysis Population	All participants enrolled and with at least one administration of IP, will be included in this study population. The Full Analysis Population will be used to analyze the primary efficacy and safety endpoints

Note: Other populations may be defined in the SAP.

### 9.4. Statistical Analyses

The statistical analysis plan (SAP) will be finalized prior to database lock and it will include a more technical and detailed description of the statistical analyses described in this section. This section is a summary of the planned statistical analyses of the most important endpoints including primary and key secondary endpoints. In case of a discrepancy, the SAP will supersede the protocol.

#### **9.4.1. General considerations**

An alpha of .05 will be used for statistical significance for all statistical tests. All statistically significant multivariate analyses will be followed by univariate post-hoc tests. Appropriate multiple comparison adjustments will be made if needed. A Last Observation Carried Forward (LOCF) method will be utilized to impute missing data where appropriate.

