### Disclosure Statement:

This is a single-group supportive care study with one arm and no masking.

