### 2.3. Significance

This study aims to capture changes in functional impact, including but not limited to the assessment of the interictal burden of migraine after participants begin treatment with fremanezumab-vfrm. In addition to using a variety of scales to capture these changes this study will use activity trackers to allow detailed monitoring of daily activity and sleep patterns. This approach has been used in a variety of clinical trials over a wide range of disease states with success and its addition will enrich the results obtained through administration of traditional questionnaires. Specific assessments of worry, work productivity, and self-efficacy will

complement the overall impact of patients' lives directly and indirectly related to response to CGRP blockade. It is hypothesized that participants treated with fremanezumab-vfrm will demonstrate improvements in a variety of measures of daily activity and attitudes. Results from this study will be a significant contribution to the medical literature and bring value to providers as they manage expectations with patients regarding the functional impact of fremanezumab-vfrm on migraine prophylaxis efforts. Moreover, this study aims to bridge the gap between the traditional focus on reduction of migraine days as a primary endpoint and the numerous other significant health and lifestyle burdens also associated with migraine and associated symptoms.

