### 5.1. Inclusion Criteria

Participants are eligible to be included in the study only if all of the following criteria apply:

1. willing to participate and sign informed consent;
2. ability to read and understand informed consent and study procedures, including able to use the electronic Daily Headache Diary;
3. in good general health based on investigator's judgment;
4. must be between 18 to 65 years of age, inclusive, at time of Visit 2;
5. have migraine with and/or without aura meeting the diagnostic criteria listed in the International Classification of Headache Disorders 3rd edition (ICHD-III; Appendix 5);
6. verification of headache frequency through prospectively collected baseline information during the 28-day screening/baseline phase reporting 4-22 migraine days and no more than 22 total headache days;
7. onset of migraine before age 50;
8. able to differentiate migraine from other primary headache types allowed in the study (e.g., tension-type headache);
9. stable history of migraine at least 3 months prior to screening with at least some discreet headache free periods;
10. not currently taking a migraine preventive OR has been taking a stable dose of a preventive for at least 90 days prior to screening and agrees to not start, stop, or change medication and/or dosage during the study period;  
\* \* participants on migraine preventive should have stable headache pattern
11. women may be included only if they have a negative pregnancy test at screening and baseline, are sterile, or postmenopausal. Women of childbearing potential (WOCBP) engaging in potentially procreative intercourse must use highly effective birth control methods for the duration of the study (i.e., starting at screening). Definitions of WOCBP, sterile and postmenopausal women, male contraception, and highly effective and acceptable birth control methods are to be determined based on investigator's judgment;

12. demonstrated compliance with the electronic Daily Headache Diary during the 28-day screening/baseline phase as defined by entry of headache data on a minimum of 23 days;
13. is willing to wear activity/sleep tracker throughout the duration of the trial;
14. has a smartphone and willing to install activity tracker app on phone.

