## 7. Discontinuation of Study Intervention and Participant Discontinuation/Withdrawal

### 7.1. Discontinuation of Study Intervention

In rare instances, it may be necessary for a participant to permanently discontinue (definitive discontinuation) study intervention. If study intervention is definitively discontinued, the participant will not remain in the study. See the SoA for data to be collected at the time of discontinuation of study intervention and for any further evaluations that need to be completed.

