### 7.2. Participant Discontinuation/Withdrawal from the Study

- A participant may withdraw from the study at any time at his/her own request, or may be withdrawn at any time at the discretion of the investigator for safety, behavioral, compliance, or administrative reasons. This is expected to be uncommon.
- At the time of discontinuing from the study, if possible, an early discontinuation visit should be conducted, as shown in the SoA. See SoA for data to be collected at the time of study discontinuation and follow-up and for any further evaluations that need to be completed.
- The participant will be permanently discontinued both from the study intervention and from the study at that time.
- If the participant withdraws consent for disclosure of future information, the sponsor may retain and continue to use any data collected before such a withdrawal of consent.
- If a participant withdraws from the study, he/she may request destruction of any samples taken and not tested, and the investigator must document this in the site study records.

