#### **8.1.2. Migraine Days via Daily Headache Diary (DHD)**

Headache and Migraine data will be recorded by the participants into an electronic daily headache diary (DHD) throughout the study. The DHDs are web-based and can be completed on any internet enabled device. Participants will be given their unique DHD URL at Visit 1. Site personnel will be responsible for instructing participants on the requirement for timely and daily completion of the DHD. Participants will be asked to record diary data each day for the previous day (24-hour period). If a participant does not experience a headache in the previous 24-hour period, the diary must still be completed as instructed. Participant's diaries may vary day to day based on their responses. All participants should have at least 80% compliance with diary completion throughout the length of the study. Participants will record headache severity, symptoms, use of acute medications, as well as additional assessments as required.

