## 9. Statistical Considerations

### 9.1. Statistical Hypotheses

The null hypothesis of this study is that participants' global Migraine Interictal Burden Scale (MIBS-4) scores will not be statistically different between 50% responders and non-responders from baseline (Visit 2) to any 4-week treatment period during the 12-week treatment period after 3 months dose of 225 mg fremanezumab-vfrm.

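### Carrying the last score forward freezes early MIBS-4 values and can turn a dropout without post-dose data into a zero-change non-responder; an observed-score mixed model and a labelling rule are a cheap improvement

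*Combined protocol and SAP*

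**What the plan says.** Missing data are covered by one sentence in section 9.4.1: "A Last Observation Carried Forward (LOCF) method will be utilized to impute missing data where appropriate". No other method is named, and nothing says when it is appropriate or whether a pre-dose value may be carried.

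Section 9.3 places everyone with at least one dose in the Full Analysis Population used for the primary endpoint. Section 9.4.2 compares 50% responders with non-responders by a repeated measures ANOVA interaction. Section 9.1 sets the contrast "from baseline (Visit 2) to any 4-week treatment period during the 12-week treatment period", so Visit 2 is the pre-dose score.

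On early leavers, section 7.1 states: "If study intervention is definitively discontinued, the participant will not remain in the study". Section 7.2 adds: "At the time of discontinuing from the study, if possible, an early discontinuation visit should be conducted, as shown in the SoA". The schedule of activities marks MIBS-4 at that visit.

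Two diary standards appear, and neither is tied to the analysis. Inclusion criterion 12 requires run-in compliance "as defined by entry of headache data on a minimum of 23 days". Section 8.1.2 says: "All participants should have at least 80% compliance with diary completion throughout the length of the study". No text defines a 50% responder or says how someone who leaves early is labelled. Section 9.4 describes itself as a summary and leaves detail to a SAP due before database lock; no separate SAP text is in the supplied document.

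**The concern.** One imputation rule can set both the outcome and the group. A participant with no MIBS-4 score after Visit 2 has only the pre-dose score to carry, so change is zero at every period. If the run-in migraine count is carried as well, the reduction in migraine days is 0% and the label is non-responder. Such participants pull the non-responder mean towards no change. That widens the responder contrast if observed non-responders improve, does nothing if they are unchanged, and narrows it if they worsen.

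A second route needs no labelling error. Because scores stop with treatment, carrying forward holds a Visit 3 value through Visit 5. If dropouts are mainly non-responders and MIBS-4 is still improving, the contrast widens again.

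The responder contrast is the primary result. The plan states: "This is a single-group supportive care study with one arm and no masking". Since the SAP may be finalised at any time before database lock, the label of a dropout could be settled with MIBS-4 scores in view. Section 2.3 expects that "participants treated with fremanezumab-vfrm will demonstrate improvements in a variety of measures of daily activity and attitudes", but it does not name MIBS-4, so overall MIBS-4 improvement is an assumption below.

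**Working it through.** **Plan's own figure.** Inputs from section 9.2: f = 0.25, alpha 0.05, power 0.95, roughly equal groups, 10% withdrawal. Four measurements are inferred from section 9.1 (Visit 2 plus three periods). Correlation 0.5 and sphericity are assumed.

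- Noncentrality = f² × N × m / (1 − rho) = 0.0625 × 36 × 4 / 0.5 = 18, with 3 and (36 − 2) × 3 = 102 df. Power = 0.952 (0.939 at N = 34).
- 36 / 0.9 = 40. Both planned figures reproduce.
- For a constant post-baseline gap g, the interaction f is g × √3 / 8, so f = 0.25 means g = 1.155 SD.

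**No-data dropouts labelled non-responder.** Take 40 participants split 20:20, both groups improving by D (in SD), no true difference. If four dropouts drawn from both groups all lack post-dose data, the non-responder group averages 18 observed + 4 carried = 22. The false gap is D × 4/22: 0.18 SD at D = 1.0 and 0.27 SD at D = 1.5, or 16% and 24% of 1.155 SD. Simulated type I error of the planned test (20,000 trials per cell, simulation error about ±0.3 points):

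| No-data dropouts among the 4 | D = 1.0 | D = 1.5 |
|---|---|---|
| 0 | 5.2% | 5.2% |
| 1 | 5.1% | 5.1% |
| 2 | 5.7% | 6.1% |
| 3 | 6.5% | 8.0% |
| 4 | 7.9% | 10.6% |

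With dropout spread over the three periods, the false gap is 0.06 to 0.10 SD and type I error 5.4 to 5.7%. If all four no-data dropouts come from the non-responders, the gap is D × 4/20, and 5,000-trial runs gave 8.5% at D = 1.0, 11.8% at 1.5 and 16.9% at 2.0. The result therefore grows with an improvement that the documents do not give. Leaving no-data dropouts unclassified while keeping LOCF returns 0.00 SD and 4.9 to 5.2%.

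**Correct labels, early scores frozen.** Four of 20 non-responders leave after Visit 3.

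- Improvement 0.5/1.0/1.5 SD at Visits 3/4/5: false gap at Visit 5 = 4/20 × (1.5 − 0.5) = 0.20 SD; type I error 7.6% (7.0% at correlation 0.3, 9.4% at 0.7).
- Improvement reaching only 1.0 SD: 4/20 × 0.67 = 0.13 SD; 6.4%.
- Two such dropouts, first pattern: 2/20 × 1.0 = 0.10 SD; 5.6%.
- Four dropouts at random: 0.00 SD; 5.0%.

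**Observed-score mixed model.** With unstructured covariance and Kenward-Roger df, the same cases gave 0.00 SD and 4.9 to 5.2%. At the planned gap of 1.155 SD with non-responders improving 1 SD, for four no-data / two no-data / spread dropout:

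- LOCF with the non-responder label estimates 1.34 / 1.25 / 1.22 SD; the mixed model estimates 1.16 in each.
- Mixed-model power is 93.2 / 94.2 / 94.7% excluding the unclassified, and 94.1 / 94.7 / 95.0% counting them as non-responders.

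**The case against.** The harm through labelling needs several things at once. LOCF must be judged appropriate for a pre-dose score; run-in counts must also be carried; the dropout must have neither post-dose diary entries nor an early discontinuation MIBS-4; three or four of four dropouts must be like this; and MIBS-4 must improve by about 1 SD. The diary is daily, so such a person must leave almost at once. Section 7.1 calls permanent discontinuation rare and section 7.2 expects withdrawal to be uncommon. The SAP may settle the rule. All of this stands, and it is why the point is not rated higher.

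It is also fair that a labelling rule alone removes the first effect, so the mixed model is not needed for that part. The model earns its place on the second route, where correct labels still leave 6.4 to 7.6% at correlation 0.5. That is itself a specific pattern, and the gain is modest.

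A reader might infer that the plan makes every dropout a zero-change non-responder, or that the primary test runs at 8 to 11% error. The documents support neither: no text says that a pre-dose value is carried or how a dropout is labelled, and the higher figures need every condition above. Nor is 11% a ceiling, because the improvement is assumed.

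**Conclusion.** The point holds as a cheap improvement of minor to moderate weight. On the supplied text, LOCF is the only named missing-data method, all dosed participants are in the primary contrast, and early leavers have no labelling rule. With the planned 4 dropouts in 40, correlation 0.5 and no true difference, type I error stays near nominal (5.4 to 5.7%) when dropout is spread. It reaches about 8 to 11% at 1.0 to 1.5 SD improvement only if all four lack post-dose data and are labelled non-responders. With correct labels it is about 6 to 8% if four non-responders leave after Visit 3 while scores keep improving.

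The direction is not fixed: the contrast is inflated only if non-responders improve. The correlation, the improvement and the dropout patterns are assumptions. The conclusion covers only the supplied text, since a SAP may add the missing rule. It would be wrong to read this as invalidating the study.

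**What to change.** 1. **Section 9.4.2.** Test the same group-by-visit interaction with a REML mixed model for repeated measures on observed MIBS-4 scores at Visits 2 to 5 (group, visit, group-by-visit; unstructured covariance; Kenward-Roger df). Keep LOCF with repeated measures ANOVA as a sensitivity analysis.
2. **Section 9.4.1.** Do not carry pre-dose MIBS-4 scores or run-in migraine counts forward. Classify responders from observed post-dose diary days prorated to 28 days. Fix the response period and the minimum number of diary days before anyone is classified, using the plan's own completeness standards. The two agree over 28 days: 80% of 28 is 22.4, so 23 whole days. Under assumed migraine rates, 23 days reproduces the full 28-day label in about 91 to 94% of participants.
3. **Section 9.3.** Report how many cannot be classified. Run the mixed model both excluding them and counting them as non-responders, so that the Full Analysis Population is respected, and name in advance which run is primary.
4. **Early discontinuation scores.** Use such a score only for the visit window in which it was collected, with windows written down beforehand. Moving it to a later visit brings carry-forward back: in the late-improvement case above, a score still at Visit 3 level entered as Visit 4 biases Visit 4 by 0.10 SD and Visit 5 by 0.025 SD.

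The cost is wording and some programming, with no new data, visits or participants. Power is about 93 to 95% against the planned 95% (LOCF with a labelling rule keeps 95.3 to 96.4%), a few dosed participants may be unclassified, and the model assumes data missing at random. The change does not address the separate issue that the groups are formed by a post-baseline outcome.

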#### **9.4.2. Primary endpoint**

Data for the primary endpoint will be statistically analyzed via a repeated measures ANOVA, within-between interaction comparing baseline MIBS-4 scores to treatment month(s) MIBS-4 scores between 50% responders and non-responders.

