### 9.2. Sample Size Determination

To determine the needed sample size for this study we utilized G\*Power Version 3.1.9.3 to conduct a power analysis for the Primary Endpoint analysis (repeated measures ANOVA, within-between interaction) comparing baseline MIBS-4 scores to treatment month(s) MIBS-4 scores between 50% responders and non-responders. Based on prior research, we expect an approximate equal proportion of responders and non-responders in this open-label study. The power analysis indicated that a total of 36 subjects would be adequate to detect a medium effect ( $f= 0.25$ ), with alpha set at 0.05, and a power of .95. To account for a 10% early withdrawal rate, a total of 40 subjects should be enrolled in the study.

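### Does leaving the 50% responder factor undefined in the protocol undermine the primary test and its stated 95% power?

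*Combined protocol and SAP*

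**What the plan says.** Section 9.4.2 analyses MIBS-4 by a "repeated measures ANOVA, within-between interaction comparing baseline MIBS-4 scores to treatment month(s) MIBS-4 scores between 50% responders and non-responders". The same split appears in the objectives and endpoints (section 3), the null hypothesis (9.1) and the power calculation (9.2).

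Section 9.2 gives 36 participants for f = 0.25, alpha 0.05 and power 0.95. On group sizes it says "we expect an approximate equal proportion of responders and non-responders in this open-label study", and on attrition "To account for a 10% early withdrawal rate, a total of 40 subjects should be enrolled in the study".

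Four other provisions bear on who is classified and how:

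- Analysis population (9.3): "All participants enrolled and with at least one administration of IP, will be included in this study population".
- Missing data (9.4.1): "A Last Observation Carried Forward (LOCF) method will be utilized to impute missing data where appropriate".
- Stopping treatment (7.1): "If study intervention is definitively discontinued, the participant will not remain in the study".
- Deferral to the SAP (9.4): "The statistical analysis plan (SAP) will be finalized prior to database lock", and "In case of a discrepancy, the SAP will supersede the protocol".

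The supplied document holds only the section 9 summary. No separate SAP is included.

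**The concern.** The group factor decides who is compared with whom, and the text gives only its label. It does not state the variable, the response window (12-week average, last month, at least two of three months, or status that changes monthly), the rule for missing diary days, or the group for a participant who leaves early. Withdrawals will need some rule, because 10% are expected, those who stop treatment leave the study, and everyone dosed stays in the analysis population.

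Two consequences would matter if they held. First, the 0.95 power might belong to one definition and not to another equally reasonable one, so that two definitions could give opposite verdicts on the same data. Second, the SAP need only be final before database lock and the study is open label. The text therefore does not exclude settling the definition with outcomes accessible, which could raise the type I error.

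**Working it through.** **1. Reproduce the stated sample size.** From section 9.2: f = 0.25, alpha = 0.05, two groups of about equal size, N = 36. From the visit schedule: m = 4 measurements (Visits 2 to 5). Assumed, because not stated: correlation rho = 0.5 and sphericity (epsilon = 1).

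- Noncentrality: lambda = f² × N × m / (1 − rho) = 0.0625 × 36 × 4 / 0.5 = 18.0
- df1 = (2 − 1)(4 − 1) = 3; df2 = (36 − 2)(4 − 1) = 102
- Power from the noncentral F = 0.952
- Enrolment: 36 / (1 − 0.10) = 40

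Both figures reproduce.

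**2. Does power depend on the definition through group size?** Holding the mean difference between groups fixed, lambda is multiplied by 4p(1 − p), where p is the responder share.

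| Responder share | lambda | Power at N = 36 |
|---|---|---|
| 50% | 18.00 | 0.952 |
| 48% | 17.97 | 0.951 |
| 53% | 17.94 | 0.951 |
| 40% | 17.28 | 0.943 |
| 30% | 15.12 | 0.908 |
| 20% | 11.52 | 0.807 |

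In the main simulations (step 3) the 12-week-average and month-3 definitions both gave shares of 48-53%, where the loss is about 0.001. A share of 30% needs a demanding rule: in a separate simulation, response in every month gave 0.30. That would depart from the roughly equal split expected in 9.2.

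**3. Does it depend on the definition through who is classified?** This can only be simulated under assumptions. Those used were a 50% median reduction in migraine days, month-to-month noise, MIBS-4 correlation 0.5, and a true link between MIBS-4 change and migraine-day reduction.

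- With the link set so that the 12-week average has about 95% power, month 3 has 77-93%. It moves 5-8 of 36 participants to the other group and gives the opposite verdict in 9-21% of trials.
- With the link set in a separate rebuild so that month 3 has 92-96% power, the 12-week average has 97-100% and opposite verdicts fall to 4-9%.

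Nothing in the document favours either starting point. The results show that a noisier classification is less sensitive. They do not show that the power in 9.2 is wrong, because 9.2 is conditional on a standardised effect of 0.25 between the two groups, however they are formed.

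**4. Type I error.** With no true link, the 12-week average fixed in advance rejected in 4.7-5.4% of simulated trials. Keeping the smallest p-value among those of seven definitions that gave 40-60% responders raised this to 12-15%.

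**5. Withdrawals.** With 4 of 40 leaving, last observation carried forward, one fixed definition and no true link, the rejection rate was 5-6% when withdrawals were spread evenly. It reached 5-11% only if all four left before Visit 3 without an Early Discontinuation MIBS-4 and the whole cohort improved by 0.5-1.5 SD. The schedule of activities includes MIBS-4 at that visit, and section 7.2 asks for the visit where possible.

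**6. What the document does settle.** Sections 2.2 and 2.3 describe reduction in migraine days as the traditional measure of prevention. Inclusion criterion 6 sets a prospective 28-day baseline of migraine days. Section 8.1.2 collects them daily throughout and asks for at least 80% diary completion. The metric and baseline can therefore be inferred with fair confidence. The window, missing days and withdrawals are what remain open.

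**The case for a change.** The strongest case for a change is that the primary result cannot be reproduced from this text alone. Accepting migraine days as the metric still leaves several windows, and an approximately equal split does not choose between them, since the 12-week average and month 3 both produce it. Section 9.1 refers to any 4-week period and 9.4.2 to one or more treatment months, so neither fixes when status is set. With no masking and a SAP that may be finalised as late as database lock, the definition could be written with results accessible. A few lines of text would close this at almost no cost.

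The omission and the permitted timing both stand. Three things weaken the case for treating them as a defect. Section 9.4 describes itself as a summary and places technical detail in the SAP, so silence here does not show that the definition is missing from the plan, and database lock is a latest date. No particular definition is shown to be better than what the analysts would choose. A rerun power calculation would return 36 again, because the document offers no effect size other than f = 0.25. The type I inflation needs selection among definitions after seeing results, and nothing points to that.

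**Conclusion.** No change to the plan follows. The response window, missing-day rule and classification of withdrawals are absent from the supplied text. They are details that an analyst would fill sensibly, most naturally as a 50% reduction in migraine days against the 28-day run-in, and section 9.4 assigns such detail to the SAP.

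The stated figures are sound on their own terms: power is 0.952 at N = 36, at least 0.943 for responder shares of 40-60%, and 40 enrolled allows for 10% withdrawal. A single pre-fixed definition holds about 5% type I error. The 12-15% rate is a worst case that requires picking the most favourable definition.

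The power figures rest on four measurements, correlation 0.5 and sphericity, none of which section 9.2 states. The error rates rest on simulation assumptions and show a range, not a prediction. The conclusion would need another look only if the SAP proved to contain no definition, or if one had been chosen after post-dose results were reviewed.
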